3.3.2.7 Oxygenation - Pulse Oximetry

Oxygenation via pulse oximetry will be assessed continuously prior to, during, and immediately following each 6MWT. Pulse oximetry will include the measurement of saturation peripheral capillary oxygenation (SpO₂) and HR. The SpO₂ and HR obtained immediately prior to and immediately following each 6MWT will be recorded in the subject's source documents and the eCRF. In addition, the lowest recorded SpO₂ and associated HR obtained during each 6MWT will be recorded in the subject's source documents and eCRF.

Study sites must use the same pulse oximeter model from Study RIN-PH-304 to maintain consistency and facilitate documentation of oxygen saturation.

In the event of Sponsor-approved telemedicine visits, oxygenation assessments will not be performed.

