^c The visit window for the Week 6 Visit is ± 3 days; the visit window for all Quarterly Visits is ± 14 days. Study visits are scheduled based on the date of enrollment in RIN-PH-305 (eg, 6, 13, 26, 39, 52 weeks after the Enrollment Visit). An unscheduled visit may occur at any time and involve any of the procedures deemed appropriate by the Investigator.

^d For females of childbearing potential, a urine pregnancy test should be done at the Enrollment Visit (prior to study drug administration) and serum pregnancy tests at all other visits.

^e Vital signs (weight, RR, HR, and BP) and ECG are to be performed after a 5-minute period of seated rest. No other measurement or procedure should be performed during this 5-minute rest period. When possible, vital signs and ECGs should be collected prior to the 6MWT.

^f See Appendix 15.2. The subject should be asked to rate their maximal breathlessness during the 6MWT immediately following the 6MWT.

^g See Appendix 15.1. All 6MWTS performed after enrollment will be conducted following at least 10 minutes of seated rest and between 10 to 60 minutes after study drug administration. The 6MWT will be conducted by qualified, trained staff in a designated 6MWT area. Subjects receiving supplemental oxygen during any 6MWT should continue to receive the same flow rate at all subsequent 6MWTS. The supplemental oxygen flow rate (L/min) must be recorded at each study visit, as applicable.

^h Pulse oximetry will be performed continuously prior to, during, and immediately following each 6MWT. Pulse oximetry will include the measurement of SpO₂ and HR. The SpO₂ and HR obtained immediately prior to and immediately following completion of the 6MWT will be recorded in the eCRF. In addition, the lowest recorded SpO₂ and associated HR obtained during each 6MWT will be recorded in the eCRF.

ⁱ PFTs will include the evaluation of FEV₁, FVC, TLC, and DLCO. TLC and DLCO will be assessed only when clinically feasible. When possible, PFTs should be performed prior to the 6MWT. If PFTs cannot be performed prior to the 6MWT, they should be performed after recovery from the 6MWT. If PFTs are done both pre- and post-bronchodilator use, only the post-bronchodilator values will be recorded.

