3.3.2.2 Vital Signs

Vital signs will be collected at all study visits after at least 5 minutes of seated rest. No other measurement or procedure should be performed during the rest period. When possible, vital signs should be collected prior to the 6-Minute Walk Test (6MWT). Vital signs to be collected include weight, respiratory rate (RR), heart rate (HR), and systolic and diastolic blood pressure (BP). Any clinically significant changes from the Enrollment Visit should be reported as AEs.

In the event of Sponsor-approved telemedicine visits, vital sign assessments will not be performed.

3.3.2.3 12-Lead Electrocardiogram

A 12-lead ECG will be recorded at all study visits after at least 5 minutes of seated rest. No other measurement or procedure should be performed during the rest period. When possible, the ECG should be collected prior to the 6MWT. Recordings should include Lead II as a rhythm strip, at least 5 QRS complexes, rhythm, HR, PR interval, QT interval, QRS duration, and any abnormalities. Any clinically significant changes from the Enrollment Visit should be reported as AEs.

In the event of Sponsor-approved telemedicine visits, 12-lead ECG assessments will not be performed.

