3.3.2.9.1 Supplemental Oxygen Use at Rest

The amount of supplemental oxygen (L/min) required at rest will be assessed at all study visits. Any changes in the amount of supplemental oxygen required at rest should be recorded in the subject's source documents and on the concomitant medication eCRF page. Supplemental oxygen should not be introduced after enrollment, unless there is a medical need in the clinical judgement of the Investigator; however, if supplemental oxygen is started after enrollment, the flow should be consistent for all subsequent tests where oxygen is required at rest.

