7.3 QUARTERLY VISITS

Subjects are to return to the study site quarterly (± 14 days). The following sequence of assessments is recommended:

- Vital signs: weight, RR, HR, and BP (following at least 5 minutes of seated rest; no other measurement or procedure should be performed during the rest period)
- 12-lead ECG (following at least 5 minutes of seated rest; no other measurement or procedure should be performed during the rest period)
- PE
- Serum pregnancy test (females of childbearing potential)
- Blood draws for clinical laboratory assessments and NT-proBNP (NT-proBNP must be drawn prior to the 6MWT and study drug administration)
- [REDACTED]
- PFTs (performed before the 6MWT or after recovery from the 6MWT)
- Study drug administration
- Pulse oximetry (measured continuously prior to, during, and following the 6MWT)
- 6MWT (following at least 10 minutes of seated rest and between 10 to 60 minutes after study drug administration) with documentation of supplemental oxygen requirement, if applicable
- Borg dyspnea score (immediately following the 6MWT)
- Confirm proper use and capture of actigraphy, spirometry, and PGA data (up to Quarterly Visit 4 [Year 1] or the Discontinuation Visit [whichever occurs first])
- Assess for AEs
- Assess for changes in concomitant medications
- Dispense study drug/device accessories and assess drug accountability/compliance

In the event of Sponsor-approved telemedicine visits, only the actigraphy, spirometry, PGA, AE, concomitant medication, and drug/device assessments will be performed.

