10.3.1 Safety Analyses

The Safety Population will be defined as all subjects in the study that receive inhaled treprostинil at any time during the course of the study. Safety analyses will be performed on the Safety Population. Treatment-emergent AEs and changes in PEs, vital signs, ECGs, clinical laboratory assessments, PFTs, at-home spirometry, and oxygenation will be the primary assessments of safety. All reported AEs will be assigned Preferred Terms per the Medical Dictionary for Regulatory Activities.

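### An onsite visit at which the 6MWT is not started yields no required SpO2, although oxygenation is among the primary safety assessments

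*Combined protocol and SAP*

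**What the plan says.** Section 3.3.2.7 ties oximetry to the walk: "Oxygenation via pulse oximetry will be assessed continuously prior to, during, and immediately following each 6MWT". The SpO2 and heart rate values "obtained immediately prior to and immediately following each 6MWT will be recorded", and the lowest SpO2 during the walk is recorded as well. No other SpO2 field is described.

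Table 3-1 gives pulse oximetry its own row, marked at every visit, but footnote h defines it in the same way: "Pulse oximetry will be performed continuously prior to, during, and immediately following each 6MWT". The checklist in Section 7.3 lists "Pulse oximetry (measured continuously prior to, during, and following the 6MWT"), and Sections 7.2 and 7.7 do likewise for Week 6 and Discontinuation.

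Vital signs offer no other route to a saturation. Section 3.3.2.2 says: "Vital signs to be collected include weight, respiratory rate (RR), heart rate (HR), and systolic and diastolic blood pressure (BP"). Section 3.3.2.9.1 adds a related item that needs no walk: "The amount of supplemental oxygen (L/min) required at rest will be assessed at all study visits". That item is a flow rate, not a saturation.

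On the status of the measure, Section 10.3.1 says: "Treatment-emergent AEs and changes in PEs, vital signs, ECGs, clinical laboratory assessments, PFTs, at-home spirometry, and oxygenation will be the primary assessments of safety".

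**The concern.** A measure named among the primary safety assessments is collected only as part of an exercise test that the protocol classes as efficacy. Nothing says what to do about oximetry when a subject attends the clinic but does not start the walk. Sections 3.3.2.5 and 7.2 to 7.7 let lung function tests go ahead without reference to whether a walk was possible; oximetry has no such freedom.

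The subjects affected are unlikely to be a random sample. Section 3.3.3.2 presents the 6MWT as a measure of exercise ability in chronic respiratory disease, so inability to start one plausibly tracks worsening. If so, the oxygenation tables at each visit describe the subjects who were well enough to walk, and a fall in saturation among the others goes unrecorded. A value that was never recorded cannot be recovered at analysis. The remedy therefore belongs in data collection, not only in the SAP.

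**Working it through.** The plan states no figure on this point, and Section 10.2 says there was no formal sample size calculation, so there is nothing to reproduce. The check has two parts: a reading of the text, and an illustration of size on assumed inputs.

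**Step 1. Which SpO2 values are required in each situation?**

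| Situation | Required SpO2 | Source |
|---|---|---|
| Onsite, walk completed | Pre-walk, lowest, post-walk | 3.3.2.7; Table 3-1 footnote h |
| Onsite, walk started, subject stops to rest | The same three; the clock keeps running and the test counts | 3.3.2.7; Appendix 15.1 |
| Onsite, walk not started | None defined | 3.3.2.7, footnote h, 7.2, 7.3, 7.7; not in vital signs (3.3.2.2, footnote e) |
| Telemedicine | None; expressly not performed | 3.3.2.7 |
| Unscheduled | Only if the investigator chooses | 7.6 |

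The third row is the gap. It concerns only subjects who never start the walk.

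**Step 2. Does another provision fill it?** The separate row in Table 3-1 and the general statement in Section 3.3 that safety assessments take place at all visits point towards a value at each visit. Neither defines one: the row's own footnote sends the reader back to the walk. Resting oxygen flow, lung function tests and adverse events do not depend on the walk, but none of them measures saturation.

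**Step 3. Illustration of size.** Let m be the share of subjects at an onsite visit who do not start the walk, and d the mean SpO2 change in non-walkers minus that in walkers. With walkers' mean change W:

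- true mean = (1 - m) x W + m x (W + d) = W + m x d
- reported mean = W
- reported minus true = -(m x d)

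The documents give neither m nor d. With assumed m of 5% to 20% and d of -2 to -5 points:

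- low end: 0.05 x 2 = 0.1 points too favourable
- high end: 0.20 x 5 = 1.0 point too favourable

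On the approximate enrollment in Section 3.5, 5% to 20% is about 7 to 27 of 136 subjects (6.8 to 27.2), or about 16 to 63 of 314 (15.7 to 62.8). These counts assume that everyone is still in the study and seen onsite. If d is zero, there is no bias in the mean.

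**The case against.** The strongest reply is that the text is silent, not prohibitive. Oximetry has its own row at every visit, Section 3.3 calls for safety assessments at all visits, and the only stated waiver is for telemedicine. A site could take a reading without a walk. This stands in part: it would be wrong to infer that SpO2 cannot be obtained at such a visit. What is missing is a requirement and a defined value.

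The second reply is that the affected group is narrow, and this stands. A reader might infer that anyone who struggles with the walk is lost, but subjects who start and rest still contribute. A reader might also infer that a new need for oxygen at rest rules out the walk. The documents do not support that: Section 3.3.3.2.1 provides for walks with oxygen started after enrollment. Appendix 15.1 is less permissive where the baseline walk was without oxygen, and the two should be reconciled, but neither cancels the test.

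Third, a reader might see a further fault in the absence of a pre-dose SpO2, since after enrollment the walk follows study drug by 10 to 60 minutes. No section promises a pre-dose value, and consistent post-dose timing is a legitimate choice. A switch to pre-dose readings could also make follow-up less comparable with the pre-walk reference from the Study RIN-PH-304 final visit, whose timing relative to dosing these documents do not give.

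Fourth, deterioration is also visible through adverse events, respiratory rate, lung function and resting oxygen flow. That is true and limits the harm, but oxygenation is listed alongside these as an assessment in its own right.

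Finally, the full SAP, the eCRF guidelines and the Study Procedures Manual are not among the documents. A reason field for missed walks or a missing-data rule may exist there. That could explain the gaps, but could not supply a saturation that was not measured.

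**Conclusion.** The point holds for onsite visits at which the walk is not started: the protocol requires no SpO2 there, and Section 10.3.1 relies on that measure. Confidence in the reading of the text is high. The consequence is less certain. That non-walkers are deteriorating is a reasonable inference, not something the documents show, and no missed-walk rate is given. The 0.1 to 1.0 point range rests wholly on assumed values. Even the sign of d is not assured, because saturation at rest depends on oxygen flow, which may have been raised.

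A reader might go further and put a figure on the share of desaturation events that would be missed. Any such figure would only restate its assumptions. Nor is this an error in alpha or power: Section 10.3 plans no hypothesis tests. What is at stake is a descriptive safety summary that may look too favourable. The point merits an amendment because the gap falls on a named safety measure, is plausibly informative, cannot be filled later, and is cheap to close.

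**What to change.** Amend Sections 3.3.2.7, 7.2, 7.3 and 7.7 and Table 3-1 footnote h as follows.

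- Record a resting seated SpO2, with the oxygen flow at that moment, at every onsite visit whether or not a 6MWT is done.
- When a walk is done, let the existing pre-walk value serve as the resting value.
- When it is not done, take the reading after the same seated rest (at least 10 minutes) and, where possible, at the same timing relative to study drug as the pre-walk value. Record the time since the last dose, so that the two kinds of reading stay comparable.
- Record the reason whenever no 6MWT is done.

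In the SAP, summarise resting SpO2 separately from the lowest value during the walk and the post-walk value, and report SpO2 availability by visit.

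The cost is one short reading at visits without a walk, with an oximeter the site must already have, and a few eCRF fields. No extra visit or device is needed. The change does not recover exertional lows in subjects who do not walk, SpO2 at telemedicine visits, or data lost to discontinuation, and the report should say so.

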3.3.2.8 Adverse Events

Adverse events that are ongoing at the final visit for Study RIN-PH-304 should be recorded in the eCRF as continuing in this study and followed as instructed below.

Subjects should be assessed for AEs from the time they sign the Informed Consent Form (ICF) until study discontinuation or completion. Subjects should be questioned for AEs at all study visits, including telephone contacts and telemedicine visits, and instructed to report all AEs upon occurrence.

All AEs should be followed until resolution (or return to normal/baseline), until they are judged by the Investigator to no longer be clinically significant, or for at least 30 days if the AE is ongoing at the final study visit.

All serious adverse events (SAEs) should be followed until resolution, death, or the subject is lost to follow-up, even if the SAE is ongoing more than 30 days after the final study visit.

Section 9 and Appendix 15.3 provide guidelines and definitions for the reporting and recording of AEs, respectively.

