7.7 DISCONTINUATION VISIT

This visit is required if the subject cannot be seen during a regularly scheduled study visit (ie, Week 6 or Quarterly Visit) to undergo discontinuation procedures. If possible, the subject should remain on study drug until completion of the discontinuation procedures. The following sequence of assessments is recommended:

- Vital signs: weight, RR, HR, and BP (following at least 5 minutes of seated rest; no other measurement or procedure should be performed during the rest period)
- 12-lead ECG (following at least 5 minutes of seated rest; no other measurement or procedure should be performed during the rest period)
- PE
- Serum pregnancy test (females of childbearing potential)
- Blood draws for clinical laboratory assessments and NT-proBNP (NT-proBNP must be drawn prior to the 6MWT and the last study drug administration, if possible)
- [REDACTED]
- PFTs (performed before the 6MWT or after recovery from the 6MWT)
- Study drug administration
- Pulse oximetry (measured continuously prior to, during, and following the 6MWT)
- 6MWT (following at least 10 minutes of seated rest and between 10 to 60 minutes after the last study drug administration, if possible) with documentation of supplemental oxygen requirement, if applicable
- Borg dyspnea score (immediately following the 6MWT)
- Confirm capture of actigraphy, spirometry, and PGA data
- Assess for AEs
- Assess for changes in concomitant medications
- Collect study drug and perform final drug accountability

- Collect the Tyvaso Inhalation System, actigraph, spirometry, and smart devices
- Complete the Discontinuation Form

The study site should complete a Discontinuation Form at the end of the subject's participation in the study, regardless of the visit type.

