8 STUDY TERMINATION

8.1 CRITERIA FOR SUBJECT WITHDRAWAL

Subjects may voluntarily withdraw from the study at any time, for any reason after completing a formal and written withdrawal of consent. Subject withdrawal of consent would preclude data collection after the date the withdrawal of consent was documented.

The Investigator should make every effort to perform all scheduled evaluations prior to study discontinuation.

A positive pregnancy test or verbal confirmation of pregnancy will result in a subject's withdrawal from the study. Refer to Section [9.4.2](#) for information related to the reporting and following of pregnancy.

In the event a subject discontinues study drug prematurely due to an AE, the subject will be followed, as instructed in Section [9.3](#). The study site should complete a Discontinuation Form at the end of the subject's participation in the study, regardless of the visit type.

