9.2 DOCUMENTATION OF ADVERSE EVENTS

All AEs will be documented from the time of informed consent until study completion or early termination. Any AE occurring during the study must be documented in the subject's source documents and on the appropriate eCRF page. Information relating to the AE such as onset and cessation date and times, intensity, seriousness, relationship to study drug, and outcome is also to be documented in the eCRF. Refer to Appendix 15.3 for guidelines and definitions for recording AEs. Where possible, AEs should be recorded using standard medical terminology. If several signs or symptoms are clearly related to a medically defined diagnosis or syndrome, the diagnosis or syndrome should be recorded on the eCRF page, not the individual signs and symptoms.

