9.3 FOLLOW-UP OF ADVERSE EVENTS

Supplemental measurements and/or evaluations may be necessary to fully investigate the nature and/or causality of an AE. This may include additional laboratory tests, diagnostic procedures, or consultation with other healthcare professionals. Applicable eCRF pages should be updated with new or additional information, as appropriate.

All AEs should be followed until resolution (or return to normal/baseline), until they are judged by the Investigator to no longer be clinically significant, or for at least 30 days if the AE is ongoing at the final study visit.

All SAEs should be followed until resolution, death, or the subject is lost to follow-up, even if the SAE is ongoing more than 30 days after completion of the final study visit.

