10.1 DATA PROCESSING

The eCRF is the primary data collection instrument for the study. All data requested in the eCRF must be recorded following the eCRF completion guidelines provided to the study site. Data will be entered in the eCRF for all subjects who sign an ICF up until study completion or discontinuation. Data recorded in the eCRF should be consistent with source documents. A representative from the Sponsor will verify eCRF data fields against source documents per the established monitoring plan. Data transmitted from the study site will be reviewed by the Sponsor and data clarification requests may be generated in the eCRF, as appropriate. The eCRF screens are to be reviewed by the Investigator for completeness and accuracy. The Investigator must electronically sign each subject eCRF to signify their approval of the data. The Investigator will be required to re-sign an eCRF if changes are made by the study site after the Investigator initially signs the eCRF. The clinical database will be final when all outstanding queries are resolved and all data management quality assurance procedures are complete.

Additional data resulting from actigraphy, spirometry, and PGA will be transmitted to the Sponsor from the respective vendors during the study and at study completion.

These data will be reviewed by the Sponsor accordingly, but will not be recorded in the eCRF. These data will be merged into the clinical database after completion of the study.

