12.2 INFORMED CONSENT REQUIREMENTS

Before a subject is enrolled in the study, the Investigator or their designee(s) must explain the purpose and nature of the study, including potential benefits and risks, and all study procedures to the subject. The subject must sign and date an IRB/IEC-approved ICF prior to the conduct of any study-related activities. A copy of the signed consent form will be given to the subject and the original will be retained in the study site's records.

The subject should also be informed that if they wish to withdraw from the study any time, a written withdrawal of consent will be required.

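### New adverse events and deaths need not be collected after a subject leaves, possibly from the day of the last dose, and the written-withdrawal rule conflicts with SAE follow-up

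*Combined protocol and SAP*

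**What the plan says.** **New events.** Section 3.3.2.8 states: "Subjects should be assessed for AEs from the time they sign the Informed Consent Form (ICF) until study discontinuation or completion". Section 9.2 agrees: "All AEs will be documented from the time of informed consent until study completion or early termination". Section 10.1 sets the same limit for data entry: "Data will be entered in the eCRF for all subjects who sign an ICF up until study completion or discontinuation". The last column of Table 3-1 is the Discontinuation Visit. About that visit, Section 7.7 says: "If possible, the subject should remain on study drug until completion of the discontinuation procedures".

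**Ongoing events.** Sections 3.3.2.8 and 9.3 follow an AE that is ongoing at the final visit for at least 30 days if it has not resolved or lost clinical significance. For serious events, Section 9.3 says: "All SAEs should be followed until resolution, death, or the subject is lost to follow-up", and it continues past 30 days where needed.

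**Withdrawal.** Section 8.1: "Subjects may voluntarily withdraw from the study at any time, for any reason after completing a formal and written withdrawal of consent". Section 12.2 has subjects told that "if they wish to withdraw from the study any time, a written withdrawal of consent will be required". The effect is in Section 8.1: "Subject withdrawal of consent would preclude data collection after the date the withdrawal of consent was documented".

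**Context.** Long-term safety and tolerability is the primary objective (Section 2.1), and treatment-emergent AEs are among the primary safety assessments (Section 10.3.1). Section 3.1 says a high rate of discontinuation is possible. Section 10.4 lets the sponsor tabulate and publish data while the study runs. Section 10.3 leaves analysis methods to the SAP; the rules at issue here govern collection and are fixed in the protocol.

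**The concern.** Two collection rules combine badly with a safety objective.

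- There is no period after the last dose in which a new SAE or death must be sought. A subject who completes the Discontinuation Visit on drug and has a first serious event a few days later has no route into the data, because nothing was ongoing at the visit.
- The only route described for voluntary withdrawal is the one that stops all data collection. No intermediate choice is offered, such as leaving visits while allowing the site to learn the outcome of an SAE or whether the subject is alive. If the subject withdraws with an SAE open, the site cannot satisfy both Section 8.1 and Section 9.3.

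If subjects who are getting worse tend to leave before the serious event, rates computed on time in study come out too low. Without follow-up of leavers, nobody could tell whether that had happened. Section 1 says the condition carries higher mortality than COPD alone, so the missed events may matter.

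**Working it through.** **1. The text, by type of exit**

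| Situation at exit | New SAE or death afterwards | SAE already ongoing |
|---|---|---|
| Leaves or completes, consent not withdrawn | Not collected (3.3.2.8, 9.2, 10.1) | Followed to resolution, death or loss to follow-up (3.3.2.8, 9.3) |
| Written withdrawal of consent | Not collected (8.1) | Conflict: 8.1 bars it, 3.3.2.8 and 9.3 require it |
| Stops drug because of an AE, stays in study | Collected while in study on the reading of 3.6 and 15.3 discussed below; 8.1 names only the follow-up of 9.3 | Followed (9.3) |

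The gap is the middle column of the first two rows. The contradiction is the last cell of the second row.

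**2. Person-time not observed (dropout assumed)**

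The plan has no figure to reproduce: Section 10.2 reports no sample-size calculation, and no dropout or death rate is given. Inputs from the documents are N = 136 or 314 (Section 3.5) and about 3 years (Section 3.6). If a fraction d leaves by year 3 at a constant rate, deaths not counted, then h = −ln(1−d)/3 and observed person-years = N(1−e^(−3h))/h = N·d/h.

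- d = 0.3: h = 0.1189. For N = 314, 314 × 0.3/0.1189 = 792 of 942 person-years. For N = 136, 343 of 408. Unobserved: 15.9%.
- d = 0.1, 0.5, 0.7: unobserved 5.1%, 27.9%, 41.9%.

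This shrinks counts of events. It does not by itself bias rates.

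**3. What selective leaving could do (all rates assumed)**

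Stable subjects die at m0 = 0.03 per year and worsen at w = 0.15. Worsened subjects die at k = 3 and leave at e. Unrelated exit is u = 0.2 in both states, and the course after exit is unchanged.

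S(t) = exp(−(m0+w+u)t); W′ = wS − (k+e+u)W; in-study hazard = (m0·S + k·W)/(S+W); Kaplan-Meier (KM) mortality at 3 years = 1 − exp(−∫hazard); rate = in-study deaths/person-years. The truth sets e = u = 0: 38.6% and 15.9 per 100 person-years.

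| e per year | KM, 3 years | Rate per 100 PY | Deaths missed after such exits, of 314 (of 136) | Of the 314, within 30 days of exit |
|---|---|---|---|---|
| 0 | 38.6% | 15.5 | 0 | 0 |
| 1.5 | 30.7% | 11.8 | 24 (10) | 6 |
| 3 | 26.0% | 9.8 | 37 (16) | 9 |
| 6 | 20.8% | 7.7 | 50 (22) | 12 |

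The table assumes that no worsened leaver has an SAE that is still followed. If a share g does, replace e by e(1−g). For e = 1.5, 3, 6:

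- g = 0.5: KM 34%, 31%, 26%.
- g = 0.8: KM 37%, 35%, 32%.

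Other assumed levels, with g = 0 and the same three values of e:

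- m0 = 0.02, w = 0.10: truth 28%, KM 22%, 18%, 14%.
- m0 = 0.05, w = 0.20: truth 49%, KM 40%, 35%, 29%.

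In the base case, extending follow-up 30 days past exit raises KM only to 33%, 29%, 25%, since about a quarter of the missed deaths fall in that period (6 of 24).

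**The case against.** The strongest reply is that the gap is narrower than it first looks. Most of that reply stands.

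- A reader might infer that every death after exit is lost. It is not: a death from an SAE ongoing at an exit without withdrawn consent is followed under Sections 3.3.2.8 and 9.3. Subjects close to death will often have such an SAE.
- A reader might infer from Section 10.1 that the eCRF closes at exit. Section 9.3 has its pages updated with new information, and Section 9.4.1 requires follow-up SAE information there, so it stays open for that purpose.
- A reader might equate stopping drug with leaving. Section 3.6 ends participation at withdrawal, death, loss to follow-up or study end; Section 8.1 does not call stopping for an AE a withdrawal of consent; and Appendix 15.3 has a code for AEs starting after permanent discontinuation of treatment.
- The conflict can be read as a specific rule (8.1) limiting a general one (9.3). That is a reasonable reading, but nothing in the protocol says so.
- The documents plan no mortality endpoint or Kaplan-Meier analysis, and deaths long after the last dose are hard to attribute to study drug. The 3-year mortality figures therefore illustrate a mechanism and are not a stated result of the trial.
- No SAP text is available, so one cannot say that the SAP ignores the problem. Exposure-adjusted rates and bounds could describe the loss. They could not restore events that were never collected.

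What remains is the absence of any window for new events after exit, and the absence of a choice between leaving and full withdrawal.

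**Conclusion.** The point holds in a limited form. Followed exactly, the protocol collects no new SAE or death after a subject leaves, and that can be the day of the last dose. For a subject who withdraws consent with an SAE ongoing, its rules conflict. Data belonging to the primary safety objective can be lost, possibly selectively.

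The size cannot be established. If leaving is unrelated to worsening, KM is unchanged and the rate moves only from 15.9 to 15.5 per 100 person-years. If worsening subjects leave, the base illustration gives 21% to 31% against a true 39% when none has a followed SAE, and 32% to 37% when 80% do. The first range is best read as a worst case for those assumed rates.

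A reader might infer that the trial's safety results will be biased low by some such amount. The documents do not support that: they give neither the rates nor any evidence that leaving depends on risk. The point should be fixed, but it does not undermine the study.

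**What to change.** 1. Reconcile Sections 8.1 and 12.2 with 3.3.2.8 and 9.3. Distinguish stopping drug, leaving visits and full withdrawal of consent. Let a subject who leaves permit limited follow-up (SAE outcome, vital status), and record the choice and the reason on the Discontinuation Form.
2. State one fixed period after the last dose in which new SAEs and deaths are collected by telephone. The 30 days already used for ongoing AEs is a natural example. Word it identically in Sections 3.3.2.8, 9.2 and 10.1 and in Table 3-1.
3. Where consent and local law allow, record vital status at study end for subjects who left. Report these deaths separately and not as treatment-emergent.
4. In any tabulation under Section 10.4, show the number leaving and their reasons, and list deaths in study apart from deaths in the post-dose period.

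The cost is a protocol and consent amendment, about one call per leaver, and the vital-status check in item 3. Subjects who fully withdrew consent remain a gap. Only data collection and reporting change; no treatment or stopping rule is affected.
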